12.3.3 Population

Pregnant daily smokers (pregnancy gestation 12-24 weeks) who would like help to stop smoking and who are willing to be randomly assigned to receive either nicotine patches or an electronic cigarette (EC) as part of their treatment. They must also be willing to receive 6 weekly support calls over the phone plus two follow-up calls, one at the end of pregnancy and one 3 months post birth.

12.3.4 Vulnerable participant's considerations N/A

12.3.5 Written/ reading / translation considerations

Participants must be able to speak and read English to allow data collection.

12.3.6 Participants lacking capacity N/A

12.3.7 Minors

12.3.8 Consenting process

Participants will be provided with the Participant Information Sheet (PIS), and will be given sufficient time to consider the PIS and entry into the trial. When they see the research team, they will be asked to confirm they have read the PIS and will be invited to ask any questions they may have. Should the participant have any questions needing medical input or wish to speak to the PI, this will be arranged. If they are happy to be involved they will be asked to read through the consent form and to initial against each of the relevant statements to confirm their agreement. They will then be asked to print their name, sign and date, and the person taking consent will do the same. The original will be retained for the Investigator site file and a copy given to the participant for their own records and a copy for the pregnancy notes. The research team member will then update the consent log with the participant's details. The local PI will review and counter sign consent and confirm eligibility before the study product is dispensed.

12.4 Screening Procedures

Once consented, participants will be asked the eligibility questions to re-confirm their eligibility (see inclusion/exclusion criteria) in cases where pre-screening was either not done in full, or it was not done immediately before consenting. This is to check that nothing changed since pre-screening, to the day of consent.

Those not eligible to take part in the study but interested in obtaining help with stopping smoking will be referred to local stop smoking services as per standard practice. The research team will document these participants on the ineligible log.

12.4.1 Eligibility assessment

Once a participant has been randomised into the study, the local PI will be notified and asked to confirm their eligibility. They will confirm via their medical notes that the patient is between 12-24 weeks pregnant and is not deemed to be having a high-risk pregnancy. The local PI will then sign the consent form to confirm that consent has been taken as per protocol and to confirm eligibility; a copy will be placed in their medical notes. It will also be recorded on the e-CRF. If a patient is not eligible following the PI assessment, they will be notified and withdrawn from the trial. This will be recorded on the e-CRF and in their medical notes.

12.5 Patient Allocation

12.5.1 Randomisation Method

Consenting individuals will be randomized to one of the two treatment groups by an electronic database created by the Barts CTU. Randomisation will not be stratified by study site as we do not expect treatment outcomes to vary by site. Blocks of random sizes will be used. More details on the randomisation algorithm used will be provided in a study-specific SOP.

12.5.2 Randomisation Procedure

Consented and eligible participants will be randomised to a treatment arm at their baseline visit. A secure online database created by the Barts CTU will be used. This will incorporate an online case report form (CRF) that will generate a unique randomisation number. This number will be added to the randomisation log by the research team. The treatment allocation will be provided immediately by the program, which will also be added to the randomisation log.

A back-up randomisation procedure will be available during working hours (0900-1700) for occasions where access to the network or internet is unavailable. In this scenario, the research team will be able to email or fax completed CRF's to the CTU for a telephone randomisation. Details on this procedure will be provided in a study-specific SOP.

12.6 Blinding

N/A

12.7Unblinding N/A

12.8 Trial Schedule

12.8.1 Schedule of Treatment for each visit

The following data will be collected and interventions delivered:

Baseline visit:

Demographic information, smoking history including whether participants live with other smokers, cigarettes smoked per day (cpd), nicotine dependence, previous stop smoking attempts and medication use, saliva sample to assess anabasine and cotinine levels to measure baseline smoke and nicotine intake, contact details of family and friends (to assist with follow ups where participants' contact details change).

Following randomization, a member of the research team will demonstrate how to use the allocated product. Further details on each intervention are described next. The research team will also arrange a suitable time for the first call from the stop-smoking advisor.

Once participants are randomised into the trial and the local PI confirms eligibility, the participants will be under the care of the local PI and staff at the trial co-ordinating centre, (HAL, QMUL).

Intervention details:

The initial and further supplies of patches or EC will be by mail, accompanied by behavioural support over the telephone.

Nicotine Patch: The study will use 15mg/16hr nicotine patch or 10mg/16hr for smokers who find the former too strong. They will be advised to wear one patch a day during waking hours as per its medicinal license. Medication will be posted form the QM main site. This is an open label RCT where the nicotine patches, a product available OTC, are being used within their medicinal licensing and so there are no special labelling or packaging requirements. The medication will be stored at the site in facilities that meet the requirements of GCP. The facilities for storage of the medication will be checked to ensure that the drug will remain stable and will be stored securely. The researcher will dispense the medication in accord with the protocol and will record the batch numbers on a log. Each person will be dispensed 2-week supply of patches initially and offered further supplies over the phone for up to 8 weeks. Patches will be sent via recorded delivery.

Electronic cigarette: The study will use a TPD-approved refillable EC (Innokin Endura T18; TPD product ID: 00132-16-00001) with a tobacco flavoured e-liquid with nicotine content of 18mg (fruit flavour e-liquid will be offered in cases where participants dislike the tobacco flavour). EC are a consumer product and this is an open label trial and so there are no special labelling or packaging requirements. Each person will be dispensed the starter kit with an initial supply of e-liquid and offered further supplies over the phone for up to 8 weeks. Supplies will be sent via recorded delivery.

Dose modifications: Participants who find their products too strong will be offered 10mg nicotine patches or 11mg eliquid.

Weekly phone calls:

Participants will receive guidance on using their allocated product and support in preparation for the Target Quit Date (TQD), on the TQD, and weekly for four weeks thereafter (6 calls in total). The schedule and content of calls will follow the established protocols of pro-active telephone counselling for smokers (e.g. [44]). This support addresses issues such as planning for the quit day and how to deal with difficult situations, such as others smoking around the quitter. We will also collect smoking status and monitor use of EC and NRT and any other stop smoking medications, and adverse events. Study staff will also complete the study questionnaires with the participants.

End of pregnancy phone call (35 week gestation to ten weeks post-partum)

Smoking status; use of EC, NRT and any other stop smoking medications; adverse events. We will also collect birth and maternal outcomes with the prior consent of participants (date of birth, birthweight, gestational age, still births, miscarriage, maternal death, congenital abnormalities, neonatal and post-neonatal deaths, neonatal intensive care admission and delivery by C-section) from hospital records. Participants reporting abstinence from smoking, reduction of cigarette consumption of 50% or more, and those smoking and using NRT or EC, will be asked to provide saliva samples for cotinine and anabasine analysis. Sampling kits will be sent by post together with instructions, and self-addressed envelope for sample return. A visit will be offered if postal samples are not returned. Participants will be provide with £20 for their time in returning the saliva sample. The cut off points for classifying participants as abstainers will be cotinine < 15 ng/ml [42] for those not reporting using any nicotine product and anabasine< 1 ng/ml [43] for those reporting any NRT/EC use.

Three months post-partum phone call

Participants will be contacted to check on any adverse events to themselves or their infant since end of pregnancy, and to record smoking status and product use.

12.8.2 Schedule of Assessment (in Diagramatic Format)

	Study session									
Measures/ Procedures	Baseline	Pre TQD	TQD	TQD+1 week	TQD+2 weeks	TQD+3 weeks	TQD+4 weeks	TQD+6 weeks	Birth FU	3 month post birth FU
Informed consent + screening	Х									
Baseline questionnaire	Х									
Randomisation	Х									
Saliva sample	Х								Х	
Smoking status/CPD	Х			Х	X	X	X		Х	X
Adverse events				Х	X	X	X		Х	X
EC/NRT use				Х	X	X	X		Х	X
EC/NRT demonstration	Х									
Birth + maternal outcomes									Х	
Behavioural support		Χ	Χ	Χ	X	X	X			
Supply of EC/patches		Χ			X		X	X		

12.8.3 Trial assessments

N/A- please see schedule of assessments

12.8.4 Follow up Procedures

Participants will be contacted for 2 data collection follow up calls post intervention; one at the end of pregnancy (35 week gestation to ten weeks post-partum) and the other 3 months post-partum. Participants will be sent a text message a few days before the call is due to ask for a suitable time to call. The QM team will attempt telephone contact first. If this is unsuccessful, participants will also be contacted via text, email and letter. There may also be the opportunity for the research team at the local site to see the participant at the clinic or to arrange a home visit. If the participant is agreeable to this, the research team will collect the follow up questions and return the saliva sample.

At three months post-partum, the study team will make 3 telephone attempts to contact the participant to collect further safety and outcome data.

Preventing distress: Many women who miscarry can participate in follow up without upset; however, calls can occasionally be distressing (e.g. relatives answering after maternal death). We will not routinely exclude women who have miscarried from follow up, but the following will minimise potential distress. The co-ordinating trial office will send the local research teams a list of participants to be followed up within the next fortnight; the local research team will be asked to identify anyone they either know to have or whose medical records show them to have experienced an event which might make follow up distressing. The opinions of the local research team will be considered when deciding whether or not to attempt follow up. In addition to this, a text reminder will be sent to all participants the day before their follow up call is due. Participants may then text back if they do not wish to be called. A reminder text will also allow participants to schedule a convenient time for their call. Participants will be able to text back their smoking status if a call is not convenient.

12.9 Withdrawal criteria

Participants will be able to withdraw from the study at any time. This will not put at risk their usual medical care. Failure to be contacted as part of the study will not count as withdrawal from the trial; the only study withdrawals will be those where participants have asked to be withdrawn from all further study procedures (i.e. withdrawal of

consent). Such participants will not be replaced and data collected up to the point of their withdrawal will be used in the study analysis. At withdrawal, we would also seek permission to still use medical records data to assess safety.

Participants will be free to stop using the allocated treatment at any time. This is one of the study outcomes and will not trigger any withdrawal procedures. However, in the event of a SUSAR or SAE that is judged to be related to NRT or EC, the CI will review the case and if deemed appropriate, the participant will be advised to stop using the medication.

12.10 Early withdrawal

Participants that withdraw their consent would not be followed up at the end of pregnancy and at 3-month post-partum. Those who withdraw from treatment but agree to further follow-up, would be contacted for any remaining weekly data collection and follow-ups. Please see section Laboratories and Samples with regards to the use of saliva samples from withdrawn participants.

12.11 End of trial (EOT)

The study would be completed and the REC informed, 6 months after the final participant has been followed up for their 3m post-partum follow-up, to allow for saliva sample analysis to be completed.

13.0 Laboratories and samples

13.1 Central Laboratories

ABS laboratories will be used for cotinine and anabasine analysis. ABS laboratories are a GLP accredited contract research organisation that specialises in the quantification of drugs, metabolites and biomarkers in biological and non-biological samples.

The contact for ABS laboratories is as follows:

[name]

ABS Laboratories Ltd. [name]

Main [contact] Direct line: [name] [contact] [contact]

The Health and Lifestyle Research Unit (HAL) at QMUL, will also serve as a central laboratory, as saliva samples will be stored here for up to 3 years prior to analyses.

The contact details are as follows:

[name] and [name]

HAL, QMUL [name]

PREP protocol v4.0 3rd January 2018

[name]

[contact]

Email: [contact]

13.2 Local Laboratories

N/A

13.3 Sample Collection/Labelling/Logging

Saliva sample to assess anabasine and cotinine levels (including 3OH cotinine) will be collected by the research team at the first visit; and mailed by participants themselves or collected by the research team at the end of pregnancy. For the end-of-pregnancy sample collection, sampling kits will be sent directly to participants along with instructions on use and a self-addressed envelope. Participant will receive a text to inform them when the sample kit has been sent and a phone call to confirm receipt and guide them through sample collection if needed.

Participants will be asked to insert the saliva swab into their mouth and leave in the mouth for approximately two minutes or until saturated, and to then insert the swab into the small inner chamber of the swab storage tube and replace the cap securely.

Samples will be labelled with a participant ID number, the time point in which the sample is being collected (e.g 'baseline') and a date of when the sample was collected. The sample will be logged by the research team and sent via recorded delivery to the HAL laboratory for storage. The sample will not need to be temperature-controlled during its transfer to the HAL laboratory, as the sample is stable for up to 2 weeks before it requires freezing.

Samples collected by the research team will aim to be mailed within 24 hours, and no later than 2 weeks. Participants will be also asked to mail the samples within 24 hours of collection. Upon receipt, the samples will be logged by the QM team and stored in at -20°C in a designated freezer for biological samples. The freezer will be kept in a closed room and the temperature will be monitored. Samples will be stored for up to three years and will be send to ABS Labs together as described below.

If a participant withdraws their consent and explicitly states that they do not wish for their data collected thus far to be used, the sample will be destroyed.

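### Section 13.3 lets site-collected saliva be posted up to 2 weeks after collection, which uses up the stated 2-week unfrozen stability and leaves no time for transit to the freezer

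*Protocol*

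**What the plan says.** Section 13.3 of the Protocol governs saliva between collection and the freezer.

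- **Stability and transport.** "The sample will not need to be temperature-controlled during its transfer to the HAL laboratory", the reason given being that "the sample is stable for up to 2 weeks before it requires freezing". Samples are "sent via recorded delivery to the HAL laboratory for storage".
- **Posting, site-collected samples.** "Samples collected by the research team will aim to be mailed within 24 hours, and no later than 2 weeks".
- **Posting, self-collected samples.** "Participants will be also asked to mail the samples within 24 hours of collection". No outer limit follows.
- **Freezing.** "Upon receipt, the samples will be logged by the QM team and stored in at -20°C in a designated freezer".
- **Dating.** The label carries "a date of when the sample was collected". No maximum age at receipt is stated.

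Section 13.2 marks local laboratories as not applicable, and no freezing at site is described. The trial-specific SOP named in section 13.4 covers the later courier leg from the coordinating laboratory to the contract laboratory.

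The research team collects every baseline sample. At end of pregnancy the default is a postal kit. The team collects only when a visit is arranged because the kit did not come back (section 12.8.1), or when the woman is seen at clinic or at home (section 12.8.4). Sections 10.3.1 and 17.5 use the end-of-pregnancy result (cotinine below 15 ng/ml, or anabasine below 1 ng/ml for users of nicotine products) to validate abstinence for the primary endpoint. The baseline result anchors the secondary endpoint on change in smoke and nicotine intake (section 10.5).

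**The concern.** The stability figure and the posting limit are the same number, but they measure different intervals. Stability runs from collection to freezing. The limit runs from collection to posting. Because the sample travels at ambient temperature and is frozen only on arrival, transit time counts against the stability window, and the limit makes no allowance for it.

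A site can therefore follow section 13.3 to the letter and deliver a sample older than the protocol says is acceptable, with no deviation recorded. Some of those samples decide whether a self-reported quitter counts as abstinent in the primary analysis. Samples are stored for up to three years and analysed together at the end of the study (sections 13.1 and 13.5.1), so if sample age is not checked at receipt, a late sample may go unnoticed until then.

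**Working it through.** **Inputs from section 13.3**

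- Unfrozen stability: 2 weeks = 14 days.
- Outer limit for posting site-collected samples: 2 weeks = 14 days; the aim is 24 hours = day 1.
- Start of freezing: on receipt.

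**Input not in the documents (assumption)**

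- Transit from posting to receipt: 1 to 7 days. Any value above zero is enough for the conclusion.

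**Step 1. Slack left for transit.** Stability minus posting limit = 14 − 14 = 0 days.

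**Step 2. Day of freezing.** Day frozen = day posted + transit. Latest posting day that stays inside stability = 14 − transit.

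| Assumed transit (days) | Posted day 1: frozen on day | Posted day 14: frozen on day | Days beyond stability if posted day 14 | Latest posting day that stays within 14 days |
|---|---|---|---|---|
| 1 | 2 | 15 | 1 | 13 |
| 2 | 3 | 16 | 2 | 12 |
| 3 | 4 | 17 | 3 | 11 |
| 5 | 6 | 19 | 5 | 9 |
| 7 | 8 | 21 | 7 | 7 |

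At the 24-hour aim every row is inside the window. At the permitted limit every row is outside it.

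**Step 3. Which samples the rule governs.**

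- *Baseline:* all are collected by the research team, so the 2-week limit applies to all of them. They do not decide the primary endpoint.
- *End of pregnancy, collected by the team at a visit:* the 2-week limit applies, and the result validates the primary endpoint.
- *End of pregnancy, posted by the participant:* the 2-week limit does not apply. There is a 24-hour request with no outer bound, so stability at receipt is not assured by rule here either.

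**Step 4. Does another section close the gap?** Section 13.2 provides no local laboratory. The SOP in section 13.4 starts after the sample has been frozen. Section 13.3 has the collection date on the label and logging on receipt, which supply the data for an age check, but it states no check. Nothing elsewhere in the Protocol limits the time from collection to freezer.

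**The case against.** The best defence is that this is an edge case. The working rule is 24 hours for both routes, and at that rule there is ample margin. Only samples posted in the last days before the outer limit can breach. The rule also mainly governs baseline samples, since end-of-pregnancy saliva is normally posted by the woman herself and team collection is the secondary route. The authors may well have meant two weeks to arrival. All of this limits how often the problem can arise. It does not alter the text, which attaches the two weeks to posting, and a stated outer limit is there for the samples that miss the aim.

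A reader might infer more: that late samples lose analyte, readings fall below the cut-offs, smokers pass as validated abstainers, and the arms are affected unequally because anabasine is used only for women still on nicotine products. The documents do not support that. They state a stability limit but not what happens beyond it, how fast, in which direction, or whether the two analytes differ. Nothing links late posting to treatment arm.

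A reader might also try to size the effect by applying an assumed late share to the abstainers expected under section 17.1 (0.08 × 570 + 0.14 × 570 = 45.6 + 79.8 = 125.4). That is the wrong group. If analyte were lost, a true abstainer would still pass. The women at risk of misclassification would be smokers who report abstinence and whose sample is late, and the documents give no figure for them. The late share would itself be a guess, and the 2-week rule covers only the team-collected part of these samples.

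The detail of how late samples are analysed can properly sit in an SOP or the SAP, so its absence from the Protocol is not a fault. The fault is the numerical limit that the Protocol does state.

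**Conclusion.** The inconsistency is real and narrow. The posting limit leaves 0 days for transit within the protocol's own 14-day stability window. A compliant site-collected sample posted on day 14 is frozen 1 to 7 days too late under an assumed transit of 1 to 7 days. Samples posted at the 24-hour aim should be unaffected.

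It reaches the secondary intake endpoint through the baseline samples. It reaches the primary endpoint only through end-of-pregnancy samples that the research team collects. Participant-posted samples are a related gap, since they have no outer limit at all.

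The number of samples affected and the direction of any bias cannot be derived from the documents, and no claim about either is made here. The sample size of 1,140 is not touched. This is a small correction to a stated rule, worth making because some of the samples concerned decide the primary endpoint and the remedy costs almost nothing.

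**What to change.** In section 13.3, replace the outer posting limit with a limit from collection to freezer, applied to site-collected and participant-posted samples alike: received and frozen at -20°C within 14 days of the labelled collection date. Keep the 24-hour posting aim.

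At receipt, compare the freezing date with the collection date on the label and flag any sample that exceeds 14 days, so that a sensitivity analysis can be run without the flagged samples.

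The cost is one sentence, a date check on a log already kept, and a few flagged samples. A tighter posting deadline is not needed once the limit runs to the freezer. Routine repeat sampling is not proposed: it would push validation later, possibly after delivery, whereas section 10.3.1 times follow-up to limit the effect of post-delivery relapse.
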